#### Handling of missing data

Unless otherwise specified missing data will not be imputed. Handling of missing data will depend on the nature of the data:

- Baseline characteristics: number of patient with missing data will be reported and descriptive statistics will be computed on patients with non-missing data.
- RECIST best overall response (BOR): patients with missing or unknown BOR will be considered as failure in the overall response rate computation (see [Section 3.5.1.1](#))

- Time-to-event endpoints: appropriate statistical methods will be used to account for censored patients (see [Section 3.5.1.2](#))
- [REDACTED] laboratory data, ECG data, vital signs: number of patient with missing data will be reported and descriptive statistics will be computed on patients with non-missing data.

Missing data will simply be noted as missing on appropriate tables/listings.

## 2.2 Analysis sets

For inclusion in any analysis set it is required that a patient has correctly consented and has received at least one dose of study treatment. For those incorrectly consented patients, they will be excluded from all analysis.

The following analysis sets which will be derived prior to database lock will be used.

### Full Analysis Set

The Full Analysis Set (FAS) comprises all patients to whom study drug were assigned by randomization. According to the intent to treat principle, patients will be analyzed according to the treatment arm assigned at randomization.

The FAS2 will consist of all patients from the placebo arm who had progression per RECIST v1.1, crossed over to the LEE011 arm and received at least one dose of LEE011.

Note that patients who were screened and are eligible but never started treatment will not be included in the FAS and FAS2.

The FAS and FAS2 will be used for all listings of raw data of placebo and LEE011 arm, and LEE011 crossover arm, respectively. Unless otherwise specified, FAS will be the default analysis set used for all summary tables and figures.

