All data collected during the optional crossover to LEE011 from placebo will be listed separately. This data will be summarized within the planned analyses. The data will not be pooled with the data from patients receiving LEE011 from the outset of the study unless otherwise specified below. Data collected after progression on LEE011 (in the situation which a patient continues to receive the study drug due to clinical benefit) will be listed but will not be pooled in analyses with data collected prior to disease progression.

Further details of statistical analysis and reporting will be described in the RAP.

For screen failure patients the eCRF data collected ([Section 7.1.1.2](#)) will not be included in any analysis but will be reported in the CSR as separate listings.

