10.1 Analysis sets

10.1.1 Full Analysis Set

The Full Analysis Set (FAS) comprises all patients to whom study drug were assigned by randomization. According to the intent to treat principle, patients will be analyzed according to the treatment arm assigned at randomization.

The FAS2 will consist of all patients from the placebo arm who had progression per RECIST and crossed over to the LEE011 arm and received at least one dose of LEE011.

FAS will be the primary population for the analysis of efficacy endpoints.

[REDACTED]

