10.2 Patient demographics/other baseline characteristics

Demographic and other baseline data will be summarized descriptively by treatment arm for the FAS and FAS2. Categorical data will be presented as frequencies and percentages. For continuous data, mean, standard deviation, median, 25th and 75th percentiles (if appropriate), minimum, and maximum will be presented.

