**Table 2-2 Summary of protocol deviations leading to exclusion from analysis sets**

Analysis set	Protocol deviations [severity codes leading to exclusion]
Full analysis set	Patient not correctly consented [8] Patient who did not receive at least one dose of study drug [8]
Full analysis set 2	Patient who did not receive at least one dose of study drug [8]
Safety set	Patient not correctly consented [8] Patient who did not receive at least one dose of study drug [8] Patient has no safety assessments (including no record that No adverse event occurred) [5]

[8] exclude from all analysis / [5] exclude from all safety analyses / [1] exclude from per protocol set / [ ]

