## 3 Statistical methods used in reporting

Data will be summarized with respect to demographic and baseline characteristics, and safety observations using descriptive statistics (quantitative data) and contingency tables (qualitative data). They will be reported using FAS.

Categorical data will be presented as frequencies and percentages. For continuous data, mean, standard deviation, median, 25th and 75th percentiles, minimum and maximum will be presented.

Listing will be reported separately for:

- (a) Patients randomized in placebo arm, until they stop to switch to LEE011 or discontinued the study, whichever occurs first
- (b) Patients randomized in LEE011 arm
- (c) Patients who crossover to LEE011 arm from the time of first LEE011 dose

Summary tables will be reported only for patients in (a) and (b) specified above.

Listings of all raw data will be produced and ordered by treatment arm, center, country and patient. Unless otherwise specified, if multiple measurements are available for one time point (or period), an average will be provided to represent the time point (or time period). Unless specified otherwise, all percentage is with respect to big N.

Screen failure patients are those who signed the informed consent, but never started the study treatment for any reason. For these patients, the only information collected on the eCRF is the screening log and the demography pages. These will not be included in any analysis, but will be reported in the CSR as separate listings.

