### **3.6 Safety evaluation**

The assessment of safety is based on the type of AEs and frequency of AEs as well as on the number of laboratory values that fall outside of pre-determined ranges (Common Toxicity Criteria [CTC] version 4.03 grading limits or normal ranges as appropriate).

The Safety set will be used for summaries and listings of all safety data in Section 14 of the CSR. Safety analyses will be performed per treatment received (see [Section 2.1.1.2](#)). The FAS will be used for Section 16 of the CSR, including for safety listings. These listings will be displayed per intended treatment as per all analyses performed on the FAS (see [Section 2.2](#)). Differences between treatment received and intended treatment, if any, will be provided in a listing.

The safety summary tables will include only assessments collected no later than 30 days after study treatment discontinuation. All safety assessments will be listed, and those collected later than 30 days after study treatment discontinuation will be flagged.

For patients who crossed over to LEE011, the placebo group will include all events before the date of first administration of LEE011 and will not include the 30 days are described above. While the LEE011 crossed over group will include all events after the date of first administration of LEE011 and will include the 30 days.

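### Does the RECIST-progression condition in FAS2 leave some crossover patients out of their own listings?

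*SAP*

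**What the plan says.** SAP Section 2.2 builds FAS2 from four conditions: placebo arm, RECIST v1.1 progression, crossover, and at least one LEE011 dose. The first three are in this sentence: "The FAS2 will consist of all patients from the placebo arm who had progression per RECIST v1.1, crossed over to the LEE011 arm". The same section then gives the set its use: "The FAS and FAS2 will be used for all listings of raw data of placebo and LEE011 arm, and LEE011 crossover arm, respectively". Protocol Section 10.1.1 has the same progression condition: "The FAS2 will consist of all patients from the placebo arm who had progression per RECIST and crossed over to the LEE011 arm".

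Other text about the same patients has no such condition. SAP Section 3 separates the listings into three groups, and group (c) reads "Patients who crossover to LEE011 arm from the time of first LEE011 dose". SAP Section 3.6 says that "the LEE011 crossed over group will include all events after the date of first administration of LEE011". The introduction to protocol Section 10 says: "All data collected during the optional crossover to LEE011 from placebo will be listed separately".

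FAS2 is also named for baseline data. Protocol Section 10.2 states: "Demographic and other baseline data will be summarized descriptively by treatment arm for the FAS and FAS2". SAP Section 3.2.3 keeps FAS2 for the listing only. SAP Section 2.1.2.5 resets baseline for patients who cross over after a first progression.

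**The concern.** When one document defines the same group of patients in two ways, two programmers can produce different listings. Here one definition asks for progression and the other does not.

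The difference has no effect if crossover always follows progression. Amendment 3 suggests that it may not. Its rationale says that the primary endpoint will not be reached, that ongoing patients will be unblinded, and that those on placebo may move to LEE011 if the investigator judges this to serve the patient. It states no progression requirement. Protocol Section 10.1.1 still has the RECIST condition, and SAP Section 1 says the SAP was written to Amendment 2.

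Read literally, SAP Section 2.2 would then omit a placebo patient who switched without progression from the set used to list the crossover arm, and the re-baseline rule would not cover that patient. The stake would be incomplete reporting of LEE011 exposure in a very small study.

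**Working it through.** The plan gives no figure on this point, so the check compares texts, counts the patients who could be affected, and traces which outputs depend on FAS2.

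**1. Which texts compete with the FAS2 definition?**

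- SAP Table 2-2 does not. It lists protocol deviations that remove patients from sets already defined. Its FAS2 row also omits placebo assignment and crossover, so it cannot be a membership rule.
- SAP Section 3.6 does not. It splits one patient's events in time at the first LEE011 dose.
- The protocol Section 10 introduction is a general instruction to list crossover data, and it leaves details to the analysis plan.
- Group (c) in SAP Section 3 does. It describes the same listing without the progression condition.

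The mismatch is therefore FAS2 against group (c).

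**2. When do the two select different patients?** Only when a placebo patient takes LEE011 without RECIST progression. Protocol Sections 2.2, 6.1.4 and 7.1.2 describe crossover at progression, and SAP Section 2.1.2.5 assumes it. Under Amendment 2, which the SAP follows, the two agree. The order of dates explains the rest: the last visible SAP entry is 07-Dec-2016 and Amendment 3 is 18-Aug-2017.

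**3. How many patients?** The Amendment 3 study status gives 10 enrolled and 4 on treatment. Of those 4, 1 had crossed over and 3 were blinded.

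- Upper limit through Amendment 3: 3/10 = 30% of patients.
- Lower limit: 0, because all three blinded patients could be on LEE011.
- Illustration: if each of the three had a 1/3 chance of being on placebo (the 2:1 ratio), the expected number is 3 × 1/3 = 1, and the chance of at least one is 1 − (2/3)³ = 0.70. The 1/3 is an assumption. Patients still blinded and on treatment are a selected group, and if LEE011 delays progression the placebo share among them would be lower.

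**4. Which outputs would change?**

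| Output | Set or group used | Does FAS2 membership matter? |
|---|---|---|
| PFS and secondary efficacy | Cancelled (SAP 3.4.2, 3.5, 4) | No |
| Summary tables | Groups (a) and (b) only (SAP 3) | No |
| Safety summaries and listings, CSR Section 14 | Safety Set (SAP 3.6) | No |
| Safety listings, CSR Section 16 | FAS (SAP 3.6) | No |
| Death listing | FAS (SAP 3.6.2) | No |
| Demographic and baseline listings | FAS (SAP 3.2), with FAS2 as an additional listing (SAP 3.2.3) | Only for the repeat listing |
| Dose intensity, concomitant therapy | Cancelled (SAP 4) | No |
| ECG, cardiac imaging, vital signs | Cancelled (SAP 4) | No |
| Liver function tests | Values are listed (SAP 3.6.3) | No re-baseline needed |
| Crossover-arm raw listings | FAS2 (SAP 2.2) or group (c) (SAP 3) | Yes, as a label |

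A placebo patient who switched without progression is still in the FAS, and in the Safety Set if its conditions are met. That patient's events, deaths and original baseline data are therefore reported whether or not FAS2 includes them. No visible output uses the crossover re-baseline.

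**The case for a change.** The best argument for a change is that the mismatch is in current text and is easy to remove. SAP Section 2.2 and group (c) describe the same listing differently, and no visible sentence says which one governs. Crossover after progression was already allowed before Amendment 3, and one patient had already crossed over, so the new language would add little unless it reached patients without progression. The condition in protocol Section 10.1.1 was left in place. The data needed to align the two (dosing dates and progression status) are already collected.

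Much of this stands. The wordings do differ, and the inference about Amendment 3 is reasonable. Two things weaken it. First, the operative text, protocol Sections 4.1.2 and 4.1.6, is not in the public document and may state a condition. The rationale and change list alone do not settle it, and Section 8.3, on emergency unblinding, mentions crossover eligibility only in passing. Second, the gain is very small. Changing protocol Section 10.1.1 would need a formal amendment with ethics approval under Section 12.1, and the lighter route in SAP Section 1 covers only the analysis-plan modules. Even a change confined to the SAP would alter no estimate, no summary table and no safety listing based on the FAS or Safety Set.

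**Conclusion.** The mismatch is real, but it is a wording gap left because the SAP is older than the last protocol amendment. It touches 0 to 3 of 10 patients through Amendment 3, and only in deciding who appears under the crossover heading of descriptive listings. An analyst would resolve it sensibly by listing every placebo-arm patient from the first LEE011 dose. Group (c) says this, and protocol Section 10 asks for all crossover data to be listed. No change is needed.

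This rests on three assumptions: the visible SAP is the one used for the close-out report, the redacted parts add no output that depends on FAS2 or on the crossover re-baseline, and the patient who had already crossed over did so after progression, as the protocol then described. If the last assumption is wrong, one more patient falls under the same label question and the conclusion is unchanged. No view is taken on who should cross over.

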### Safety Set

The safety set includes all randomized patients who received at least one dose of study drug, and have at least one valid post-baseline safety assessment. The statement that a patient had no AEs (on the AE eCRF) constitutes a valid safety assessment.

Patients will be classified according to treatment received, which is defined as:

- The treatment assigned if it was received at least once, or
- The first study drug received when starting therapy with study treatment if the assigned treatment was never received.

[Table 2-2](#) summarized protocol deviations leading to exclusion from analysis sets. Severity codes are defined in [\[Validation and Analysis Planning \(VAP\) Module 3\]](#). Patients were excluded from the analysis sets defined above based on the protocol deviations entered in the database.

**Table 2-2 Summary of protocol deviations leading to exclusion from analysis sets**

Analysis set	Protocol deviations [severity codes leading to exclusion]
Full analysis set	Patient not correctly consented [8] Patient who did not receive at least one dose of study drug [8]
Full analysis set 2	Patient who did not receive at least one dose of study drug [8]
Safety set	Patient not correctly consented [8] Patient who did not receive at least one dose of study drug [8] Patient has no safety assessments (including no record that No adverse event occurred) [5]

[8] exclude from all analysis / [5] exclude from all safety analyses / [1] exclude from per protocol set / [ ]

### 2.3 Interim analysis

Not applicable.

## 3 Statistical methods used in reporting

Data will be summarized with respect to demographic and baseline characteristics, and safety observations using descriptive statistics (quantitative data) and contingency tables (qualitative data). They will be reported using FAS.

Categorical data will be presented as frequencies and percentages. For continuous data, mean, standard deviation, median, 25th and 75th percentiles, minimum and maximum will be presented.

Listing will be reported separately for:

- (a) Patients randomized in placebo arm, until they stop to switch to LEE011 or discontinued the study, whichever occurs first
- (b) Patients randomized in LEE011 arm
- (c) Patients who crossover to LEE011 arm from the time of first LEE011 dose

Summary tables will be reported only for patients in (a) and (b) specified above.

Listings of all raw data will be produced and ordered by treatment arm, center, country and patient. Unless otherwise specified, if multiple measurements are available for one time point (or period), an average will be provided to represent the time point (or time period). Unless specified otherwise, all percentage is with respect to big N.

Screen failure patients are those who signed the informed consent, but never started the study treatment for any reason. For these patients, the only information collected on the eCRF is the screening log and the demography pages. These will not be included in any analysis, but will be reported in the CSR as separate listings.

### **3.1 Enrollment status**

These analyses will not be provided, since the enrollment in the study was halted after only a few patients treated. See details in Section 4.

### **3.2 Patient disposition, background and demographic characteristics**

The FAS will be used for all baseline disease characteristics and demographic summaries and data listings.

Baseline demographic, reasons for screen failure and serious adverse events will be listed for screened failure patients.

#### **3.2.1 Patient disposition**

The FAS will be used for the patient disposition summaries. Based on the four eCRF pages 'End of Treatment Phase Disposition', 'End of Post Treatment Phase Disposition', 'End of Crossover disposition' and 'End of Post Treatment Phase Disposition 2' will be combined by treatment. A listing of study completion by treatment will be produced. Patients are considered to be ongoing if they have not discontinued due to any reason (e.g., disease progression, AE, withdrawn consent).

#### **3.2.2 Protocol deviations**

These analyses will not be provided, since the enrollment in the study was halted after only a few patients treated. See details in Section 4.

#### **3.2.3 Background and demographic characteristics**

Background and demographic characteristics including age, gender, race, ethnicity, height, weight, ECOG performance status, tumor type and medical conditions will be listed and summarized using descriptive statistics. The summaries will be based on the assessments from the screening visit (baseline). The FAS and FAS2 (for listing) will be used.

In addition, the following derived variables derived from the demographic eCRF will be described:

- age groups summarized by class (<65, ≥65 years)
- Body mass index (BMI) calculated as  $\text{weight}/(\text{height}^2)$  ( $\text{kg}/\text{m}^2$ ) where weight is measured in kg and height in m

#### **3.2.4 Medical History**

These analyses will not be provided, since the enrollment in the study was halted after only a few patients treated. See details in Section 4.

#### **3.2.5 Prior antineoplastic therapy**

These analyses will not be provided, since the enrollment in the study was halted after only a few patients treated. See details in Section 4.

### **3.2.6 Diagnosis and extent of cancer**

These analyses will not be provided, since the enrollment in the study was halted after only a few patients treated. See details in Section 4.

### **3.2.7 Other baseline characteristics**

These analyses will not be provided, since the enrollment in the study was halted after only a few patients treated. See details in Section 4.

## **3.3 Treatments (study drug, rescue medication, other concomitant therapies, compliance)**

### **3.3.1 Study medication**

These analyses will not be provided, since the enrollment in the study was halted after only a few patients treated. See details in Section 4.

#### **3.3.1.1 Duration of study treatment exposure**

The following algorithm will be used to compute the duration of study treatment exposure for patients who took at least 1 dose of any of the components of the study treatment:

Duration of exposure (days) = (last date of exposure to any study treatment component) – (date of first administration of any treatment component) + 1.

Both date of first administration of study treatment and last date of exposure to study treatment are defined in [Section 2.1.3.3](#) and [Section 2.1.3.5](#), respectively.

For patients who did not take any drug the duration of drug exposure is by definition equal to zero.

### **3.3.2 Prior and concomitant medication**

These analyses will not be provided, since the enrollment in the study was halted after only a few patients treated. See details in Section 4.

## **3.4 Analysis of the primary variable(s)**

### 3.4.1 Primary variable(s)

The primary endpoint of the study is PFS, defined as the time from the date of randomization to the date of the first documented progression or death due to any cause. PFS will be assessed via the local radiology assessment according to RECIST v1.1. If a patient has not had an event, PFS will be censored at the date of the last adequate tumor evaluation [[Protocol CLEE011X2201 Appendix 1](#)].

### 3.4.2 Statistical model

The primary efficacy endpoint, PFS will be formally analyzed at the final analysis time point [[Protocol CLEE011X2201 Section 10.8](#)].

If the estimated hazard ratio at the final analysis is 0.48 or below, it will be considered as evidence of clinically relevant efficacy of LEE011 over placebo.

To claim the superiority of LEE011 to placebo, both criteria below need to be satisfied:

- The log-rank test p-value (one-sided) is below 0.05
- The estimated HR is 0.48 or smaller

The distribution of PFS between the **two treatment arms** will be compared using the log-rank test. The HR will be estimated using the Cox proportional hazard regression model. The estimated HR and related two-sided 90% confidence interval (CI) will be provided.

In addition, PFS will be analyzed using Kaplan-Meier estimates [[Kaplan and Meier 1958](#)] (including graphical representation) with two-sided 90% confidence interval for median survival and survival probabilities for specific time-points (3, 6, 9, 12, 15, 18, 21 and 24 months) will be presented for each treatment arm.

The final primary analysis of PFS will be conducted when a total of 23 PFS events are observed (See [[Protocol CLEE011X2201 Section 10.8](#)] for sample size calculation) and patients have been followed for PFS for at least 6 months or have discontinued prior to this time for disease progression or death, or have withdrawn consent to follow up or have been lost to follow up. This event number is associated with 80% power when the underlying hazard ratio is 0.33 (corresponding to 2 months median PFS for placebo versus 6 months median PFS for LEE011).

These analyses will not be provided, since the enrollment in the study was halted after only a few patients treated. See details in Section 4.

